	5.6 List of potential effect modifiers to be examined
	5.7 Future exploratory (path) analyses
7.	Design of tables and figures

Version number	Version date	Pre pare d by	Description of the completed editions
01.0	26.07.2013	[name]	Original document Appendix 05 added
01.1	16.04.2014	[name]	Updated Appendix 05 to delete detailed power calculations and to add equivalence testing for quasi-continuous outcomes. Several minor (non-substantive) corrections were made to description of variable construction. Tables are edited to defer decision on presentation of medians vs. means until by-group distributions can be examined.

1. Version history

2. Overview and study objectives

The analysis presented here is nested within a pre-existing iLiNS-DOSE analysis plan for primary and other secondary outcomes. Refer to the main analysis plan for: inclusion and exclusion criteria for the trial; data cleaning protocols; procedures for breaking code; and procedures for modifying this protocol.

The main objective of data collection related to IYCF practices is to compare practices across intervention groups. This analysis is motivated by concerns that energy-dense LNS may displace breastfeeding and/or nutrient-dense local foods and/or impede dietary diversification with local foods, thus negatively impacting infant feeding practices and development of infant dietary preferences and habits. Effects on IYCF practices could be mediated either by maternal perceptions of different needs for breast milk or local foods for infants receiving supplements and/or by a change in appetite, demand for breastfeeding, or preference for local foods among infants who consume the supplement.

Data on IYCF practices have been gathered on the full study samples, and complement quantitative dietary data and breast milk intake data, which were collected on sub-samples and at fewer time points.

IYCF practices we will compare across groups include: continued breastfeeding, frequency of breastfeeding, frequency of feeding solid/semi-solid foods¹, consumption of nutrient-dense food

¹Data are not yet available, so variable construction and analysis for these data are not described in this version of the analysis plan.

groups yesterday and last week, food group diversity. We also assessed consumption of other fortified products (other than the project LNS) but preliminary analysis of the full sample showed that consumption of such products was extremely rare among iLiNS-DOSE infants, so no further analysis is planned.

Specific objectives of analysis

1.1 Primary objective

To compare infant and young child feeding practices and summary diet quality variables across intervention groups. Comparisons at baseline are descriptive, to assess comparability of groups. At all later time points, comparisons are to assess the effect of the intervention on IYCF practices.

1.2 Secondary objectives

To create summary diet quality variable(s) for potential use in analyses of main outcomes (effect modifiers)

To provide descriptive data on IYCF practices to contextualize results of the trials, and to aid readers in comparing to IYCF in other settings

To provide supporting descriptive data for full samples for manuscripts describing dietary intake of sub-samples, and for triangulating between food frequency and dietary data.

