1.3 Exploratory analyses

Exploratory analyses will be described later, in separate SAP or in addenda to this SAP. Note that in the sister trial in Burkina Faso ("iLiNS-ZINC"), there is a pre-planned exploratory analysis: description of child feeding practices and factors associated with these practices including food security and seasonality, and relation with nutritional status (growth, iron status, morbidity).

3. Hypotheses to be tested

Stated qualitatively: Provision of LNS would not impact infant and young child feeding practices. More specifically, provision of LNS would not cause a change in:

- Breastfeeding (prevalence of any breastfeeding several time points throughout intervention, and reported frequency of breastfeeding the previous day)
- Frequency of feeding other solids foods (meals and snacks, or feeding episodes)²;

²These data are not yet available and variable construction and analyses are not described in this version.

- Dietary diversity measured as food group diversity at or above the WHO cut-off³;
- Number of nutrient-dense food groups (animal-source foods, fruits and vegetables)

4. Description of infant and young child feeding practice outcome variables

On the following pages, we present information on construction of outcome variables.

The table shows details on: data sources; variable names and variable construction; treatment of data and criteria for imputing missing values.

With few exceptions (detailed in the table) no data will be imputed for analyses of IYCF practices as outcomes.

However, in later analyses where longitudinal IYCF practice variables (e.g. indices summed across time points) may be used as potential effect modifiers, data could be imputed to avoid losing substantial numbers (those for whom data from all time points are not available).

Timing of outcomes: in the iLiNS-DOSE trial, target dates for collection of IYCF practices data were: Baseline (week 0, at ~5.5-6.5 mo of age); week 16; week 28; week 40; and endline (week 52). Data on breastfeeding practices, food group intake, and use of fortified products and vitamin/mineral drops were assessed at all time points. Data on frequency of meals and snacks were collected on KAP questionnaires at 6, 12, and 18 months of age (data not yet available).

³ WHO (2008) Indicators for assessing infant and young child feeding practices: conclusions of a consensus meeting held 6–8 November 2007 in Washington D.C., USA.

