5.7 Future exploratory (path) analyses

There are a number of potential effect modifiers not yet available, but which could interact with provision of LNS to produce differential effects. These may be included in later exploratory analyses:

- Household
 - Proxy for income (expenditures)
 - o Grandmother lives on compound/with the child
- Maternal
 - o Index for responsive feeding (composite from KAP)
 - o Maternal decision-making power (composite from KAP)
 - o Maternal depression
- Child
 - o Morbidity

o Appetite

7. Design of tables and figures

See following pages for a list of tables and example figures that will be examined by the manuscript writing group:

Table 1.	Number of observations and missing visits, by intervention group and by time point					
Table 2.	Background characteristics of study participants, baseline and endline samples, by intervention group					
Table 3.	Feeding practices at enrollment, by intervention group					
Table 4a.	Continued breastfeeding and frequency of breastfeeding yesterday, by intervention group					
(Table 4b.	Continued breastfeeding and frequency of breastfeeding yesterday, pairwise comparisons. This table, with pairwise comparisons, will be prepared if overall tests are significant)					
Table 5a	Infant diet quality yesterday: food group diversity & nutrient-dense food groups by intervention group					
(Table 5b	Infant diet quality yesterday: food group diversity & nutrient-dense food groups, pairwise comparisons. This table, with pairwise comparisons, will be prepared if overall tests are significant)					
Table 6a	Infant diet quality last week: nutrient-dense food groups, by intervention group					
(Table 6b	Infant diet quality last week : nutrient-dense food groups, pairwise comparisons This table, with pairwise comparisons, will be prepared if overall tests are significant)					
Example figures (final set of figures to be determined):						

Figure 1	Participant flow
Figure 2	Breastfeeding practices, by intervention group
Figure 3	Nutrient-dense food groups yesterday, by intervention group
Figure 4	Possibly, a Figure illustrating comparison between adjusted confidence intervals and equivalence margins

Table 1. Number of observations and missing visits, by time point (FFQ)

Age ^a	X.X mo			X.X mo			XX.X mo				XX.X mo				XX.X mo					
Group ^b	0	10	20	40	0	10	20	40	0	10	20	40	0	10	20	40	0	10	20	40
Number permanently																				
lost to follow-up																				
Number missing																				

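### Appendix 05 earmarks diet-quality variables, possibly indices summed over weeks 0 to 52, as effect modifiers for the main outcomes, while also testing whether LNS changes those feeding practices

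*SAP*

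**What the plan says.** SAP Appendix 05, 1.2 Secondary objectives, sets out "To create summary diet quality variable(s) for potential use in analyses of main outcomes (effect modifiers"). Section 4 of the appendix (description of the outcome variables) says that "longitudinal IYCF practice variables (e.g. indices summed across time points) may be used as potential effect modifiers", and that missing values could be imputed for this purpose. The collection times given there are "Baseline (week 0, at ~5.5-6.5 mo of age); week 16; week 28; week 40; and endline (week 52").

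The same feeding practices are outcomes. Under 1.1 Primary objective: "At all later time points, comparisons are to assess the effect of the intervention on IYCF practices". Section 2 (overview) gives the reason for the analysis, a concern that "energy-dense LNS may displace breastfeeding and/or nutrient-dense local foods and/or impede dietary diversification with local foods". One suggested route is "by a change in appetite, demand for breastfeeding, or preference for local foods among infants who consume the supplement".

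Section 5.7, headed as future exploratory (path) analyses, opens with "There are a number of potential effect modifiers not yet available, but which could interact with provision of LNS to produce differential effects". It lists child morbidity and appetite among them and gives no measurement time for either. By contrast, the modifiers in 5.6 are drawn from the covariates in 5.5, which are baseline values apart from child age at the visit.

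Main SAP section 12.5 stratifies the analysis of change in LAZ when an interaction reaches p<0.1. Appendix 05, 5.4, follows up interactions at p<0.05 for the feeding outcomes.

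**The concern.** An effect modifier should be fixed before treatment starts, so that within each of its levels the LNS and control children remain comparable by randomisation. An index that includes weeks 16 to 52 does not meet that condition if LNS alters feeding. Suppose LNS lowers the index. LNS children in a given stratum are then those who would have scored higher without it, and they differ from the control children beside them in whatever else goes with a better diet, such as household circumstances or health. If part of the LNS effect runs through diet, stratifying also removes some of the effect being estimated.

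At stake is objective 5 of the main SAP, which asks which characteristics modify the effect of LNS. Strata formed partly by the response to LNS cannot answer that question, and their differences could be read as LNS effects.

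**Working it through.** The SAP gives no figure for this point, so there is nothing of its own to reproduce. The logic was checked against the text and then sized under assumptions.

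**1. The texts side by side.** Appendix 05 names five feeding visits. Weeks 16, 28, 40 and 52 come after randomisation, so an index summed over all visits takes four of its five components from the intervention period. Section 1.1 treats those four visits as outcomes of LNS. Sections 1.2 and 4 treat the summed variable as a possible modifier of LNS. No sentence limits the index to week 0 or notes the timing.

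**2. Size with no true effect.** None of these inputs is in the documents. Let T be 1 for LNS and 0 for control, and let U be an unmeasured cause of both index and outcome. All are in SD units:

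- index M = aU + error − dT
- outcome Y = bU + error, with no LNS term

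Within each arm M and Y have variance 1, so the expected Y given M and T is ab(M + dT). At a fixed index value the LNS-minus-control difference is a × b × d, although the true effect is zero.

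- Mild case (a = 0.5, b = 0.3, d = 0.2): 0.5 × 0.3 × 0.2 = 0.03 SD.
- Stronger case (a = 0.6, b = 0.5, d = 0.4): 0.6 × 0.5 × 0.4 = 0.12 SD.

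A tertile is a band and not a single value, so the difference there is somewhat smaller. A simulation of 4 million children with 5/6 on LNS (six equal arms assumed) gave:

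| Case | Overall | Low | Middle | High |
|---|---|---|---|---|
| Mild | 0.00 | 0.020 | 0.027 | 0.021 |
| Stronger | 0.00 | 0.090 | 0.111 | 0.086 |

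**3. Direction.** If LNS instead raises the index by 0.2 to 0.5 SD, with an index-outcome correlation of 0.1 to 0.5 and a split at the median, the false difference within strata runs from −0.01 to −0.17 SD. The sign depends on which way LNS moves feeding.

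**4. Check of the remedy.** With d = 0, which is what a week-0 variable guarantees, the stratum differences are at most 0.003 SD with the median split. That is simulation error around zero.

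**5. Would an interaction test bring such strata to light?** In step 2 the slope of Y on M is ab in both arms, so a pure shift creates no interaction. At 1932 children with 5/6 on LNS, a test at p<0.1 rejected in 10.0 to 10.7% of 3,000 runs, close to its nominal 10%. If LNS multiplied the spread of the index by k, the slopes would differ by r(1/k − 1), where r is the index-outcome correlation. That is 0.3 × (1/0.9 − 1) = 0.03 at the mild end and 0.5 × (1/0.6 − 1) = 0.33 at the strong end. The documents do not indicate whether such narrowing is likely.

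**The case against.** Most of the case against limits the reach of the point without removing it.

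- **The use is optional and exploratory.** The text speaks of potential use in later analyses, gives no formula for the index, and defers exploratory analyses to later addenda. The main SAP calls such analyses hypothesis-generating. This stands, and it limits the weight. But creating the variables for this use is a stated objective, and an exploratory label does not remove the bias.
- **Section 12.5 does not name these indices.** A reader might infer that its p<0.1 rule will turn them into stratified growth results. The documents do not say so: 12.5 lists nine variables and two exploratory themes (maternal knowledge, attitudes and practices; household wealth), and 1.2 does not refer to it. Under a pure shift the rule would also trigger hardly more often than by chance.
- **Morbidity and appetite.** A reader might infer that 5.7 makes them post-randomisation modifiers of growth. That section follows one on modifiers of feeding practices, gives no measurement time, and already carries a path-analysis heading. What can be shown there is mixed terminology. That they are follow-up measures is likely, since objective 3 of the main SAP treats both as outcomes, but it is not stated.
- **The appendix hypothesises that LNS does not change feeding.** If that were exactly true, this bias would vanish for the feeding indices. Section 5.4 concedes, however, that the study is severely underpowered for equivalence analyses, so a non-significant difference would not justify stratifying.
- **The bias is small against sampling error.** A middle-tertile difference has a standard error of about 0.10 SD, so 0.02 to 0.12 SD is at most about one standard error. This is fair, but the bias is systematic and the sampling error is not.

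**Conclusion.** The point holds as a limited one. Sections 1.2 and 4 of Appendix 05 earmark as effect modifiers variables that may be measured largely after randomisation and that the same appendix treats as possible effects of LNS. Differences within strata of such variables are not randomised comparisons.

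Under the assumed inputs and no true effect, the false within-tertile difference is about 0.02 to 0.12 SD, with its sign set by the direction in which LNS moves the index. It rests on two conditions that the documents raise but do not quantify: that LNS shifts the index, and that index and outcome share a cause. Without the first it is zero.

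The hypothesis-driven modifier list in 12.5 and the modifiers in 5.6 are not shown to share the problem. The primary estimates and the confirmatory tests are untouched.

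**What to change.** In Appendix 05, 1.2 and section 4, state that feeding variables used as effect modifiers in analyses of LNS effects are restricted to week-0 values, which were collected. State that indices including any later visit will be used only in mediation or path analyses with their assumptions set out, and not as strata for the LNS-control comparison.

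In 5.7, align the list with its heading: if morbidity and appetite are measured after randomisation, treat them in the same way and do not call them effect modifiers.

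This needs wording only and no new data. The price is that feeding at about six months of age varies less than feeding over the whole year, so fewer modifiers may be detected.

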1.3 Exploratory analyses

Exploratory analyses will be described later, in separate SAP or in addenda to this SAP. Note that in the sister trial in Burkina Faso ("iLiNS-ZINC"), there is a pre-planned exploratory analysis: description of child feeding practices and factors associated with these practices including food security and seasonality, and relation with nutritional status (growth, iron status, morbidity).

3. Hypotheses to be tested

Stated qualitatively: Provision of LNS would not impact infant and young child feeding practices. More specifically, provision of LNS would not cause a change in:

- Breastfeeding (prevalence of any breastfeeding several time points throughout intervention, and reported frequency of breastfeeding the previous day)
- Frequency of feeding other solids foods (meals and snacks, or feeding episodes)²;

²These data are not yet available and variable construction and analyses are not described in this version.

- Dietary diversity measured as food group diversity at or above the WHO cut-off³;
- Number of nutrient-dense food groups (animal-source foods, fruits and vegetables)

4. Description of infant and young child feeding practice outcome variables

On the following pages, we present information on construction of outcome variables.

The table shows details on: data sources; variable names and variable construction; treatment of data and criteria for imputing missing values.

With few exceptions (detailed in the table) no data will be imputed for analyses of IYCF practices as outcomes.

However, in later analyses where longitudinal IYCF practice variables (e.g. indices summed across time points) may be used as potential effect modifiers, data could be imputed to avoid losing substantial numbers (those for whom data from all time points are not available).

Timing of outcomes: in the iLiNS-DOSE trial, target dates for collection of IYCF practices data were: Baseline (week 0, at ~5.5-6.5 mo of age); week 16; week 28; week 40; and endline (week 52). Data on breastfeeding practices, food group intake, and use of fortified products and vitamin/mineral drops were assessed at all time points. Data on frequency of meals and snacks were collected on KAP questionnaires at 6, 12, and 18 months of age (data not yet available).

³ WHO (2008) Indicators for assessing infant and young child feeding practices: conclusions of a consensus meeting held 6–8 November 2007 in Washington D.C., USA.

Variable construction and handling for IYCF practice outcomes

Outcome	Variable name(s)	Location, variable construction	Criteria for errors, outliers	Criteria for transformation	Use of imputation
~9.6 mo: Still breastfed (%)	Source variables: • visitid • FFqStillFed Constructed variable: • stillbf	"visitid" is a numeric variable constructed from the string variable "NumberVisit" visitid=16 Still breastfed variable is on Form 13a & 13b, page 1; new constructed variable is named stillbf to harmonize with other sites	As above	No - dichotomous	Missing data can be coded as "1" (yes) if child is reported to be still breastfed at later time points.
~9.6 mo: Breastfed 6+ times yesterday (%)	Source variables: • Visitid • FFqNumBrtFeeds Constructed variable: • bf_6	"visitid" as above Frequency of breastfeeding from Form 13a & 13b, page 1 Coded "4" or "6" (different questionnaire versions had different codes, in error; syntax recodes all to same)	As above	No - categorical	No imputation for analysis of outcomes (group comparisons)
~12 mo: Still breastfed(%)	As above	visitid=28 Else as above	As above	No - dichotomous	As above, can impute missing data if "yes" at later time points.
~12 mo: Breastfed 6+ times yesterday (%)	As above	visitid=28 Else as above	As above	No - categorical	No imputation

Outcome	Variable name(s)	Location, variable construction	Criteria for errors, outliers	Criteria for transformation	Use of imputation
~15 mo: Still breastfed (%)	As above	visitid=40 Else as above	As above	No - dichotomous	As above, can impute missing data if "yes" at later time points.
~15 mo: Breastfed 6+ times yesterday (%)	As above	visitid=40 Else as above	As above	No - categorical	No imputation
~18 mo: Still breastfed (%)	As above	visitid=52 Else as above	As above	No - dichotomous	No imputation; no later time points.
~18 mo: Breastfed 6+ times yesterday (%)	As above	visitid=52 Else as above	As above	No - categorical	No imputation

Outcome	Variable name(s)	Location, variable construction	Criteria for errors, outliers	Criteria for transformation	Use of imputation
~9.6 mo: 4+ food groups yesterday (WHO) (%)	 visitid 1. Starchy staple groups: FqLiqPorr24, FFqThobw a24, FFqPorridge24, FFqOthGrain24, FFqTuber24 2. FFqLegume24 3. Dairy groups: FFqMilk24, FFqFormula24, FFqFqMilkTea24, FFqPoirt24 4. Flesh food groups: FFqOrgan24, FFqFalsh24, FFqFlesh24, FFqFalsh24, FFqFalsh24 5. FFqEggs24 6. Vit A-rich fr/vegs: FFqVitAVeg24, FFqVitAFr24 7. Other fruits/veg: FFqOthFr24, FFqOthFr24, FFqOthVeg24 	Form 13, pages 2-3. For each of the 7 WHO food groups, a dichotomous variable is constructed, and coded "1" if any of the constituent groups=1; "0" if all are "0", missing if all are missing or combination of missing and 0. Constructed variables are: starch24, legume24, dairy24, flesh24, eggs24, vitafood24, othfrveg24 These new variables are summed to construct "dd24", a quais-continuous variable ranging from 0 to 7. A dichotomous variable is constructed for the WHO minimum diversity indicator, coded "0" if dd24<4, "1" if dd24 is 4, 5, 6 or 7, and missing if missing: dd24GE4	As above	No, dichotomous	If missing, variables for organ meats and insects are imputed to 0 as consumption was very rare (1.9% and 0.2% of child-days, respectively) No other imputation for analysis of outcomes (group comparisons)

Outcome	Variable name(s)	Location, variable construction	Criteria for errors, outliers	Criteria for transformation	Use of imputation
~9.6 mo: No ASF yesterday (%)	 visitid FFqMilk24 FFqFormula24 FFqMilkTea24 FFqYogurt24 FFqOrgan24 FFqFlesh24 FFqEggs24 FFqFash24 FFqDairy24 FFqInsects24 	Form 13a, pages 2-3 The four dairy- containing fluids are coded, along with FFqDairy, into a new summary variable for any dairy yesterday "dairy24" A dichotomous ASF variable, for any ASF yesterday: "asf24yn". Coded "1" if dairy24 or any of organ, flesh, eggs or fish=1. Coded "0" if all are 0. Coded missing if all missing or combination of missing & 0. For this outcome, reporting % w/asf24=0.	As above; for solid foods, enumerator errors included not ticking "yes" when foods were circled, and not ticking "no" when not (i.e., not completing right-hand column on page 3). These values were corrected when missing or when errors observed, but we did not do a review of 100% of forms.	No - dichotomous	If missing, variables for organ meats and insects are imputed to 0 as consumption was very rare (1.9% and 0.2% of child-days, respectively) For all other ASF variables prevalence is >5% and there is no imputation.
~9.6 mo: Number of ASF food groups yesterday	 visitid dairy24 FFqOrgan24 FFqFlesh24 FFqEggs24 FFqFish24 FFqInsects24 	Source of variables described above. The first 5 ASF variables are summed into a score, "asf24sum". A point is added for insects only if flesh foods are otherwise scored "0". Missing if any variables are missing.	As above	Quasi- continuous and non-normally distributed in full sample. No transformation planned.	As above.

Outcome	Variable name(s)	Location, variable construction	Criteria for errors, outliers	Criteria for transformation	Use of imputation		
~9.6 mo: No fruits/vegetables yesterday (%)	 visitid FFqVitAVeg24 FFqLeaves24 FFqVitAFr24 FFqOthFr24 FFqOthVeg24 	Form 13a, page 3. A dichotomous fruit /vegetable variable, for any fr/veg yesterday: "frveg24yn". Coded "1" if any of the five groups=1. Coded "0" if all are 0. Coded missing if all missing or combination of missing and 0. For this outcome, reporting % with frveg24yn=0.	As above	No - dichotomous	No imputation for analysis of outcomes (group comparisons) In full sample, prevalence of child-days coded "1" is >10% for each of the 5.		
~9.6 mo: Number of fruit/veg groups yesterday	As above	Source of variables described above. The 5 fruit/vegetable variables are summed into a score, "frveg24sum". Missing if any of the 5 are missing.	As above	Quasi- continuous and non-normally distributed in full sample. No transformation planned.	As above		
 ~12 mo: 4+ food groups yesterday (WHO) (%) ~12 mo: No ASF yesterday (%) ~12 mo: Number of ASF food groups yesterday ~12 mo: No fruits/vegetables yesterday (%) ~12 mo: Number of fruit/veg groups yesterday 	As for ~9.6 month time point						
 ~15 mo: 4+ food groups yesterday (WHO) (%) ~15 mo: No ASF yesterday (%) ~15 mo: Number of ASF food groups yesterday 		As for ~9.6 month time point					

iLiNS-DOSE: Statistical Analysis Plan, appendix 05, v 2.0

Outcome	Variable name(s)	Location, variable construction	Criteria for errors, outliers	Criteria for transformation	Use of imputation			
~15 mo: No fruits/vegetables yesterday (%)		•	-					
~15 mo: Number of fruit/veg groups								
yesterday								
~18 mo: 4+ food groups yesterday (WHO)								
(%)								
~18 mo: No ASF yesterday (%)								
~18 mo: Number of ASF food groups	As for ~9.6 month time point							
vesterday								
~18 mo: Number of fruit/yeg groups								
vesterday								
~9.6 mo: ASF score (out of 28)	 visitid FFqMeat7 FFqEggs7 FFqFish7 FFqDairy7 	Form 13a, page 4. The 4 ASF variables are summed into a score, "asf7sum". Range is 0 to 28. Missing if any are missing, or coded "66", which means the child had the food, but respondent could not say how many days in last 7 days.	Obvious enumerator and data entry errors corrected; no other changes. Uncorrectable illegal codes coded missing.	Quasi- continuous and non-normally distributed in full sample. No transformation planned.	No imputation for analysis of outcomes (group comparisons)			

Outcome	Variable name(s)	Location, variable construction	Criteria for errors, outliers	Criteria for transformation	Use of imputation
~9.6 mo: Lowest ASF tertile (%)	As above	Categorical variable "asf7T16" is constructed by creating tertiles of "asf7sum" based on the entire sample (all groups) at visit 16. The variable is coded 1-3 for lowest to highest tertile. Dichotomous variables are also generated, "i16_asfT1 – i16_asfT3" and coded 0 if no and 1 if yes for the indicated tertile. E.g. if a score is in the lowest tertile, i16_asfT1=1 and if not, i16_asfT1=0.	As above	No, constructed variables are categorical or dichotomous.	As above
~9.6 mo: Fruit/veg score (out of 35)	 Visitid FFqVitAVeg7 FFqLeaves7 FFqVitAFr7 FFqOthFr7 FFqOthVeg7 	Form 13a, page 4 The 5 fruit/vegetable variables are summed into a score, "frveg7sum". Range is 0 to 35. Missing if any are missing, or coded "66", which means the child had the food, but respondent could not say how many days in last 7 days.	Obvious enumerator and data entry errors corrected; no other changes. Uncorrectable illegal codes coded missing.	Quasi- continuous and non-normally distributed in full sample. No transformation planned.	No imputation for analysis of outcomes (group comparisons)

Outcome	Variable name(s)	Location, variable construction	Criteria for errors, outliers	Criteria for transformation	Use of imputation
~9.6 mo: Lowest fruit/veg tertile (%)	As above	Categorical variable "frveg7T16" is constructed by creating tertiles of "frveg7sum" based on the entire sample (all groups) at visit 16. The variable is coded 1-3 for lowest to highest tertile. Dichotomous variables are also generated, "i16_frvegT1- i16_frvegT3" and coded 0 if no and 1 if yes for the indicated tertile. E.g. if a score is in the lowest tertile, i16_frvegT1=1 and if not, i16_frvegT1=0.	As above	No, constructed variables are categorical or dichotomous.	As above
\sim 12 mo: ASF score (out of 28)		As for ~9.6 m	onth time point		
~12 mo: Lowest ASF tertile (%)	As above	Constructed as above. New variables are asf7T28, and i28_asfT1 through i28_asfT3.	As above		
~12 mo: Fruit/veg score (out of 35)		As for ~9.6 m	onth time point		
~12 mo: Lowest fruit/veg tertile (%)	As above	Constructed as above. New variables are frveg7T28, and i28_frvegT1 through i28_frvegT3.	As above		

Page 14	of 27
---------	--------------

Outcome	Variable name(s)	Location, variable construction	Criteria for errors, outliers	Criteria for transformation	Use of imputation			
~15 mo: Lowest ASF tertile (%)	As above	Constructed as above. New variables are asf7T40, and i40_asfT1 through i40_asfT3.	As above					
~15 mo: Fruit/veg score (out of 35)		As for ~9.6 m	onth time point					
~15 mo: Lowest fruit/veg tertile (%)	As above	Constructed as above. New variables are frveg7T40, and i40_frvegT1 through i40_frvegT3.	As above					
~18 mo: ASF score (out of 28)		As for ~9.6 m	onth time point					
~18 mo: Lowest ASF tertile (%)	As above	Constructed as above. New variables are asf7T52, and i52_asfT1 through i52_asfT3.	As above					
~18 mo: Fruit/veg score (out of 35)	As for ~9.6 month time point							
~18 mo: Lowest fruit/veg tertile (%)	As above	Constructed as above. New variables are frveg7T52, and i52_frvegT1 through i52_frvegT3.	As above					

5. Approach to analysis and exclusions specific to this analysis

All tests will be two-sided, at 5% level of significance.

Since varying numbers of observations are available depending on the time point (i.e., there were a substantial number of missed visits), sample sizes by group will be reported for each time point. If specific outcome variables are missing for more than 10% of infants (with denominator being total records available for the time point) we will report the number of observations used per specific outcome analysis.

First analysis will be by intention-to-treat, but excluding observations that are more than ± 4 weeks (28 days) from the median observed age for visits 0, 16, 28 and 40. That is, at time points, 0, 16, 28 and 40, child age could vary by up to 8 weeks.

Exclusions for visit 52 (endline) will be handled differently. For visit 52, we will exclude visits that are more than 28 days before the target date as for other time points. But since many endline visits were late, and since feeding practices change more slowly by 18 months of age compared to earlier time points, we will include visits up to 6 weeks after the target date for the child. Rationale: visit 52 was planned to occur exactly one year after the date of enrollment. However, so long as visit 52 occurred within one month of the target date, the child received a 2 week supply of LNS. So, if the endline FFQ occurred within ~6 weeks (42 days) of target, the child should have had LNS in the week prior to the FFQ.

Data on subjects who were lost to follow-up (either temporarily or permanently) will be included in the analysis for all time points where data are available.

After the intent-to-treat analysis, we will perform a per protocol analysis as follows: on the FFQ (Form 13) questionnaire itself, respondents were asked how many days in the last 7 days the child consumed LNS the household received from the project. In preliminary analysis, it is apparent that there is heavy data lumping on "0" and "7". Per protocol analysis will compare feeding practices for infants who were reported to consume LNS 7 days in the last 7 days, as compared to those who were either in the delayed intervention group, or reported to consume the supplement 0 days. Infants who were reported to consume LNS 1-6 days in the last 7 days will be excluded from this analysis (0.3-7.9% of infants, depending on time point).

After group codes are revealed, if at any time point fewer than 10% of those in the LNS groups were reported to consume on 0 days in the last 7 days, this analysis will not be performed.

6. Statistical methods

